#### **5.2.8 Sheehan Suicidality Tracking Scale (Sheehan STS)**

The Sheehan STS is a prospective, patient self-reported or clinician administered rating scale that contains 16 questions to track both treatment-emergent suicidal ideation and behaviors. The S-STS will be completed on a paper form at the site. At the screening visit, the recall period for completing the S-STS is 30 days prior; at all other visits, the recall period for completing the S-STS is since the last visit. Subjects who have a S-STS score  $> 0$  should be immediately evaluated by the investigator. If the investigator determines that a subject is at risk of suicide or self-harm, appropriate measures to ensure the subject's safety and obtain mental health evaluation must be implemented. **The event should be recorded as either an AE or SAE determined by the investigator and reported within 24 hours to the Sponsor.** Subjects with a response of 1 ("a little") to Question 2 may be allowed in the study at the Screening and/or Baseline visits and eligible to continue participation in treatment phase. Investigator's review and assessment should be documented in subject source. Subjects with a response greater than 1 on Question 2 should not be enrolled in the study.

### **5.3 Efficacy Assessments**

According to the most recent recommendations of the Initiative on Methods, Measurements, and Pain Assessment in Clinical Trials (IMMPACT), 6 core outcome domains (namely pain, physical functioning, emotional functioning, participant rating of improvement and satisfaction with treatment, symptoms and adverse events, and participant disposition) should be considered for

clinical research trials assessing chronic pain. Outcome measures for the current study were chosen in accordance with these guidelines.

### **5.3.1      *Numeric Pain Rating Scale (NPRS)***

The Numeric Pain Rating Scale is a segmented, 11-item, numeric scale ranging from 0-10. The NPRS is anchored by items ranging from “0” which represents “no pain;” to “10” which reflects “worst pain imaginable.”

Subjects will be given a paper diary to record daily pain intensity on the Numeric Pain Rating Scale. They will be asked to keep a daily record of their average pain intensity over a 24 hour period. A reduction of 2 points on the NPRS has been chosen to reflect a clinically important improvement in pain symptoms.

### **5.3.2      *Penn Facial Pain Scale***

The Penn Facial Pain Scale-Revised a 12-item scale used to assess the impact of trigeminal neuralgia pain on health-related quality of life and activities of daily living. Developers of the original Penn Facial Pain Scale applied standard validation metrics (e.g., concept elicitation, cognitive debrief, reliability, responsiveness) to the Penn Facial Pain Scale-Revised as a measure for use in assessing treatment impacts on TN symptoms. The response categories for each of the 12 items range from 0 (‘does not interfere’) to 10 (‘completely interferes’). The specified recall period is for the ‘past week.’ Anchors to scale 0 to 10 were added by Biohaven.

Subjects will be asked to complete the Penn Facial Pain Scale-Revised at the beginning and end of each treatment phase, as outlined in the Schedule of Assessments.

### **5.3.3      *Pain Disability Index***

The Pain Disability Index is designed to measure the degree to which a patient’s daily life is disrupted by their pain. The seven items of the scale reflect different “life activities” and are scored on an 11-point Likert Scale, with “0” representing “no disability” and “10” representing “worst disability.”

Subjects will be asked to complete the Pain Disability Index at the beginning and end of each treatment phase, as outlined in the Schedule of Assessments.

### **5.3.4      *Patient Global Impression of Change Scale (PGIC)***

The PGIC is a patient-rated scale which assesses how the subject’s current illness state has improved or worsened relative to the baseline visit. The subject is asked to rate a change in their overall disease condition on a 7-point scale, from 1 (‘no change’) to 7 (‘a great deal better’). The PGIC is a global index scale that may be used to rate the response of a condition to a therapy. The PGIC will be conducted at the beginning and end of each treatment phase as indicated in the Schedule of Assessments and Events.

### **5.3.5      *Rescue Medication***

The subject's use of rescue medication will be recorded daily in the paper diary. After dosing with study drug/medication, all other Trigeminal Neuralgia medication is prohibited during the 2 hours post daily dose. However, a subject who does not experience relief of the Trigeminal Neuralgia at the end of two hours after dosing, will be permitted to use the following rescue medications: aspirin, ibuprofen, acetaminophen up to 1000mg/day, Naprosyn (or any other type of non-steroidal anti-inflammatory (NSAID), antiemetics (e.g., metoclopramide or promethazine) or baclofen. These are the only medications allowed for rescue treatment after 2 hours post daily dose of study drug/medication.

### **5.3.6      *Worst Pain Episode***

Using the 11-point Numeric Pain Rating Scale (NPRS) described above, subjects will be asked to record an intensity rating of their worst pain episode over a 24-hour period daily in their paper diary.

## **5.4      Early Discontinuation from the Study**

Subjects MUST discontinue investigational product (and non-investigational product at the discretion of the investigator) for any of the following reasons:

- Withdrawal of informed consent (subject's decision to withdraw for any reason)
- Any clinical adverse event (AE), laboratory abnormality or intercurrent illness which, in the opinion of the investigator or sponsor, indicates that continued participation in the study is not in the best interest of the subject
- Pregnancy
- Termination of the study by Biohaven Pharmaceuticals
- Loss of ability to freely provide consent through imprisonment or involuntary incarceration for treatment of either a psychiatric or physical (e.g., infectious disease) illness
- Please see section [5.2.8](#) for guidance on study discontinuation based on results from the S-STS.
- Subjects who discontinue early from the Double-Blind Phase are not eligible to enter the Open-label Extension Phase.

All subjects who discontinue should comply with protocol specified Follow-Up Safety Visit procedures as outlined in [Table 1](#) or [Table 2](#). The only exception to this requirement is when a subject withdraws consent for all study procedures, lost to follow up or loses the ability to consent freely (i.e., is imprisoned or involuntarily incarcerated for the treatment of either a psychiatric or physical illness).

## 6 STUDY DRUG/MEDICATION MANAGEMENT

### 6.1 Description of Study Drug/Medication

#### 6.1.1 *Investigational Product*

An investigational product, also known as investigational medicinal product in some regions, is defined as follows:

A pharmaceutical form of an active substance or placebo being tested or used as a reference in a clinical study, including products already with a marketing authorization but used or assembled (formulated or packaged) in a way different from the authorized form, or used for an unauthorized indication, or when used to gain further information about the authorized form.

- The investigational product should be stored in a secure area according to the local regulations. It is the responsibility of the investigator to ensure that the investigational product is only dispensed to study patients. The investigational product must be dispensed only from official study sites by authorized personnel according to local regulations.
- During the Double-Blind Treatment Phase, investigational product (study drug/medication) is rimegepant (BHV-3000) 75 mg Immediate Release (IR) Tablet or matching placebo dosed daily.
- During the Open-label Extension Phase, investigational product (study drug/medication) is rimegepant (BHV-3000) 75 mg orally disintegrating tablet (ODT) dosed daily.
- All subjects, regardless of the treatment phase, will take study drug/medication daily.

**NOTE:** During the Double-blind and Open-label Extension Phase, if a dose of study drug/medication for a given day is missed, lost, or otherwise unable to be taken, the subject should document that as a missed dose on the **subject paper study log**.

#### 6.1.2 *Packaging, Shipment, and Storage*

The product storage manager should ensure that the study drug/medication is stored in accordance with the environmental conditions (temperature, light, and humidity) as determined by the sponsor. Please refer to the study specific Pharmacy Manual for specific conditions. If concerns regarding the quality or appearance of the study drug/medication arise, do not dispense the study drug/medication and contact the sponsor/CRO immediately.

### 6.2 Dose and Administration

#### 6.2.1 *Method of Assigning Subject Identification*

The investigator or designee will need to access an Interactive Web-based Response System (IWRS) in order to register each subject in the Double-Blind Treatment Phase. Initially the investigator or designee will enter the subject into the study at the Screening Visit after informed

consent is obtained and a subject number is assigned. After completion of all screening evaluations, all eligible subjects will be randomized, in a 1:1 into one of two treatment sequences to receive 75 mg IR tablet of rimegepant or Placebo, using a 2-period, 2-sequence, crossover design. Patients with atypical TN and typical TN will be stratified equally into each of the two treatment sequences, with atypical TN patients not exceeding 50 percent of the subjects.

Study Staff will access the IWRS at each scheduled study visit throughout the Double-Blind Treatment Phase. The IWRS system will assign specific bottle numbers for all blinded study drug/medication to be dispensed to the subject. Once a bottle has been assigned it cannot be dispensed to another study subject.

During the Open-Label Extension Phase, study drug/medication (ODTs) will be supplied to the sites in bulk and specific drug wallets will be dispensed outside of the IWRS by the study staff to each subject. Once a wallet has been assigned it cannot be dispensed to another study subject.

Once a subject completes the Double-Blind Treatment Phase, or if a subject is discontinued early from the study, the investigator or designee must access the IWRS to discontinue the patient from participation in the study.

### **6.2.2 Selection and Timing of Dose Administration**

During the Double-Blind Phase of the study, subjects will be randomized to a sequence of either rimegepant (75 mg QD) and then placebo or placebo then rimegepant (75 mg QD) in a 2-sequence, 2-period, crossover design. Study drug/medication will be dispensed at the baseline visit and at Days 14 and 21. Subjects should take the first dose the day of the baseline visit. Study drug/medication should be administered in the morning without regard to meals. Subjects who showed continued compliance during the Double-Blind Phase may choose to enter a 12 week Open-label Extension Phase with daily dosing of rimegepant (75 mg QD) ODT. Open-label study drug/medication will be dispensed at Day 35 visit for subjects who enter the Open-label Extension Phase. Subjects should take the first dose of OLE study drug/medication on Day 36.

During the Open-label Extension Phase, if a dose of study drug/medication for a given day is missed, lost, or otherwise unable to be taken, the subject should document that as a missed dose on the **subject paper study log**.

### **6.2.3 Dose Modifications**

There will be no dose adjustments in this study.

## **6.3 Blinding and Unblinding**

Blinding is critical to the integrity of this clinical study. However, in the event of a medical emergency or pregnancy in an individual subject, in which knowledge of the investigational product is critical to the subject's management, the blind for that patient may be broken by the treating physician.

Before breaking the blind of an individual subject's treatment, the investigator should have determined that the information is necessary, i.e., that it will alter the subject's immediate management. In many cases, particularly when the emergency is clearly not investigational product related, the problem may be properly managed by assuming that the subject is receiving active product without the need for unblinding. Unblinding will be managed via the IWRS system.

A pharmacokinetics, IWRS randomization manager, and pharmacovigilance role may be unblinded before data are more generally unblinded after the Randomized Phase of the study. Except as noted above, other members of the BHV research team will remain blinded.

In cases of accidental unblinding, contact the Medical Monitor and ensure every attempt to preserve the blind is made.

#### **6.4 Treatment Compliance**

Responsible study personnel will dispense the study drug/medication. Accountability and compliance verification should be documented in the subject's study records.

Subjects will be counseled on the importance of taking the study drug/medication as directed at all study visits. During the Double-Blind Phase, if poor compliance (i.e., multiple missed doses resulting in less than 80% overall compliance during the Double-Blind Phase), the subject will be re-counseled on proper drug adherence and should not be considered for participation in the Open-Label Extension Phase. Any subject having poor compliance during the Open-Label Extension Phase resulting in less than 80% should be re-counseled and discontinuation of the subject from the trial should be considered if adherence does not improve.

#### **6.5 Destruction and Return of the Study drug/medication**

All unused and/or partially used study drug/medication can be sent back to the drug depot for destruction only after being inspected and reconciled by the responsible BHV Study monitor or the sponsor's designee.

If it is site policy to destroy study drug/medication on site, it is the investigator's responsibility to ensure that arrangements have been made for the disposal, procedures for proper disposal have been established according to the applicable regulations, guidelines and institutional procedures, and appropriate records of the disposal have been documented. The unused study drug/medications can only be destroyed after being inspected and reconciled by the responsible BHV Study monitor or the sponsor's designee.

## **7 ADVERSE EVENTS**

An Adverse Event (AE) is defined as any new untoward medical occurrence or worsening of a pre-existing medical condition in a subject or clinical investigation subject administered an investigational (medicinal) product and that does not necessarily have a causal relationship with this treatment. An AE can therefore be any unfavorable and unintended sign (including an abnormal laboratory finding for example) symptom, or disease temporally associated with the use of the investigational product, whether or not considered related to the investigational product.

Adverse events can be spontaneously reported or elicited during an open-ended questioning, examination, or evaluation of a subject. In order to prevent reporting bias, subjects should not be questioned regarding the specific occurrence of one or more AEs.

Subjects should be instructed to notify the Investigator when a Serious Adverse Event occurs.

There are two types of adverse events, Serious Adverse Events (SAE) and Non-Serious Adverse Events (AEs).

## 8 SERIOUS ADVERSE EVENT

### 8.1 Definition of Serious Adverse Event

A SAE is any event that meets any of the following criteria:

- Death
- Life-threatening
- Inpatient hospitalization or prolongation of existing hospitalization
- Persistent or significant disability/incapacity
- Congenital anomaly/birth defect in the offspring of a subject who received BVH-3000 (Rimegepant)
- Other: Important medical events that may not result in death, be life-threatening, or require hospitalization, may be considered an SAE when, based upon appropriate medical judgment, they may jeopardize the subject and may require medical or surgical intervention to prevent one of the outcomes listed in this definition. Examples of such events are:
  - Intensive treatment in an emergency room or at home for allergic bronchospasm
  - Blood dyscrasias or convulsions that do not result in inpatient hospitalization
  - Development of drug dependency or drug abuse
  - Potential drug-induced liver injury

#### 8.1.1 ***Definition of Terms***

**Mild:** A mild adverse event is usually transient and may require only minimal treatment or therapeutic intervention. The event does not generally interfere with usual activities of daily living.

**Moderate:** A moderate adverse event is usually alleviated with additional specific therapeutic intervention. The event interferes with usual activities of daily living, causing discomfort, but poses no significant or permanent risk of harm to the subject.

**Severe:** A severe adverse event interrupts usual activities of daily living, significantly affects clinical status, or may require intensive therapeutic intervention.

**Life threatening:** An AE is life threatening if the subject was at immediate risk of death from the event as it occurred; i.e., it does not include a reaction that if it had occurred in a more serious form might have caused death. For example, drug induced hepatitis that resolved without

evidence of hepatic failure would not be considered life threatening even though drug induced hepatitis can be fatal.

Hospitalization: AEs requiring hospitalization should be considered SAEs. Hospitalization for elective surgery or routine clinical procedures that are not the result of AE (e.g., elective surgery for a pre-existing condition that has not worsened) need not be considered AEs or SAEs. If anything untoward is reported during the procedure, that occurrence must be reported as an AE, either 'serious' or 'non-serious' according to the usual criteria.

In general, hospitalization signifies that the subject has been detained (usually involving at least an overnight stay) at the hospital or emergency ward for observation and/or treatment that would not have been appropriate in the physician's office or outpatient setting. When in doubt as to whether 'hospitalization' occurred or was necessary, the AE should be considered serious.

The following hospitalizations are not considered SAEs in BHV clinical studies (but may be considered non-serious AEs):

1. A visit to the emergency room or other hospital department <24 hours that does not result in an admission (unless considered "important medical event" or event that is life threatening);
2. Elective surgery, planned prior to signing consent;
3. Admissions as per protocol for a planned medical/surgical procedure;
4. Routine health assessment requiring admission (i.e., routine colonoscopy);
5. Admission encountered for another life circumstance that carries no bearing on health and requires no medical intervention (i.e., lack of housing, care-giver respite, family circumstances).

Disability/incapacitating: An AE is incapacitating or disabling if the experience results in a substantial and/or permanent disruption of the subject's ability to carry out normal life functions.

## **8.2 Collection and Reporting Serious Adverse Events**

Following the subject's written consent to participate in the study, all SAEs, whether related or not related to study drug/medication, must be collected, including those thought to be associated with protocol-specific procedures. All SAEs must be collected that occur during the screening period and throughout the course of the study up to and including the End of Treatment Visit. The investigator should report any SAE occurring after these time periods that is believed to be related to study drug/medication or protocol-specific procedures.

All SAEs should be followed to resolution or stabilization.

An SAE report should be completed for any event where doubt exists regarding its status of seriousness.

If the investigator believes that an SAE is not related to the study drug/medication, but is potentially related to the conditions of the study (such as a withdrawal of previous therapy or a complication related to study procedure), the relationship should be specified in the narrative section of the SAE Report Form.

SAEs, whether related or not related to study drug/medication, overdose (see section [8.2.1](#)), potential drug induced liver injury (see section [8.2.3](#)) and pregnancies (see section [8.2.2](#)) must be reported within 24 hours of the Investigator becoming aware of the event. For this study we will be capturing SAEs through electronic data capture (EDC) and on the SAE form.

The Investigator is responsible for reporting all SAEs and all Other Important Medical Events to PPD within 24 hours of learning of the event. PPD will then immediately notify the Biohaven Medical Monitor of the event. The Investigator is responsible for submitting all applicable events to the Independent Review Board (IRB) as per the IRB's reporting requirements. Additionally, the Investigator, or designated staff, is responsible for submitting the SAE information to PPD (i.e.: event term, start stop dates, causality, severity).

Any serious adverse event must be reported immediately or no later than 24 hours after awareness of the event to PPD Pharmacovigilance (PVG). A written description of any serious adverse event, using the PPD SAE report form, must be sent to PPD PVG by facsimile (fax) within 24 hours after awareness of the event:

North America – [name]

If a form is unable to be submitted within 24 hours, the SAE may be reported by telephone via the Safety Hotline Number:

North America – [name]

If only limited information is initially available, follow-up reports are required. If an ongoing SAE changes in its intensity or relationship to study drug/medication or if new information becomes available, a follow-up SAE report should be sent within 24 hours of the Investigator becoming aware of the updated information using the same procedure used for the transmission of the initial SAE and the same event term should be used.

The minimum information required for an initial SAE report is:

- Sender of report (Site number, Investigator name)
- Subject identification (subject number)
- Protocol number
- SAE term (if an SAE is being reported)

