(d) Height measured at Screening Visit only. Weight, body temperature, respiration rate, blood pressure, and heart rate will be collected at all timepoints where indicated. Sitting arterial systolic and diastolic blood pressure and radial artery pulse rate will be measured.

(e) SAEs, AEs and concomitant Procedures must be reported after subject signs informed consent. SAEs should be reported from signing of consent through the 14 day follow up safety visit. Non-serious AEs should be reported from the baseline visit to the safety follow up visit.

(f) Subjects must take their study drug/medication every day, regardless of whether or not they have Trigeminal Neuralgia pain. Subjects must report each tablet they take on the paper diary. Due to the COVID-19 Pandemic, study drug/medication may be shipped to a subject, with up to an 2-week supply. Proper documentation must be maintained in the subject's source records including shipping vendor, tracking number, confirmation of receipt by subject, and all other relevant information.

(g) Subjects with 2 or more missed daily paper pain diaries during the Screening Period should be considered for discontinuation from the study for poor compliance, after discussion with sponsor. Subjects in the Double-Blind Treatment Period who demonstrate poor compliance will be discussed with the Sponsor and corrective training will be complete by the site with the subject.

(h) The paper diary will be dispensed at the Screening Visit, after all Screening Procedures are completed. The subject will be trained on the use of the paper diary. The subject will use the paper diary every day during the Screening and Double-Blind Phases to report Trigeminal Neuralgia pain, medication use and study drug/medication dosing (Double-BlindTreatment Phase only).

(i) Subjects who do not complete the Double-Blind Treatment Phase should completed the End of Treatment Visit and the 14 day Follow-up Safety Visits (they should not enter the Open-label Extension Phase).

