(j) Due to COVID-19 Pandemic, very effort should be made to conduct the study visits within the specified windows. However, if necessary due to local COVID-19 safety requirements, visits may be performed outside of these windows in order to minimize any potential risks to subject safety and to comply with governmental and institutional guidance. All procedures not able to be completed due to a visit being conducted remotely must be reported as a protocol deviation and can be performed at the next visit, where appropriate to do so based on subject presentation. See sections 3.5.1 - 3.5.3 for more information.

(k) For subjects who do not enter the Open-label Extension Phase, the follow-up visits should be scheduled based on date of their EOT Visit. The visit window for the 2 Week Follow-up Visit is 14 days (-2 / +7 days).

(l) If subject entering Open-label extension, dispense Open-label study drug/medication at day 35.

(m) If subject entering Open-label extension, dispense Open-label paper diaries.

(o) Re-screen procedures for the return of completed subjects will include all screening procedures except for the neuro exam/neuro imaging and the pain diaries

- **End of Treatment needs to be completed one (1) time, either during the double-blind treatment phase or open-label extension phase**
- All **randomized** subjects should complete the 2 Week Follow-up Safety Visit at any time they either complete or discontinue from the study with the exception of those subjects who discontinue early from the the study due to withdrawal of consent by subject, are lost to follow-up or death

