**Table 2: Schedule of Assessments- Open-Label Extension Phase**

Procedure	Open-label Extension (n)(p)			Follow-up Phase (p)(q)  2-Week Follow-up (day 133) post last dose (- 2/+7 days) (k)
	Day 63 (+/- 2 days)	Day 91 (+/- 2 days)	Day 119 (- 2 / +5 days)/ EOT Visit	
	Visit 6	Visit 7	Visit 8	
Concomitant Medications (r)	X	X	X	X
Physical Examination			X	X
Vitals Signs / Physical Measurements (d)	X	X	X	X (vital signs only)
Laboratory Assessments			X	X
Liver Function Test	X	X	X	X
Pregnancy Test (Serum)				
Pregnancy Test (Urine)	X	X	X	X
Urine Drug Screen			X	
12-Lead ECG	X	X	X	X
Serious Adverse Event Assessment	X	X	X	X
Sheehan Suicidality Tracking Scale (S-STS)	X	X	X	X
Daily Average Pain (NPRS)	X	X	X	
Patient Global Impression Change Scale (PGI-C)	X	X	X	
Pain Disability Index	X	X	X	
Penn Facial Pain Scale-Revised	X	X	X	
Record of Daily Rescue Medication	X	X	X	
Daily Worst Pain (NPRS)	X	X	X	
Dispense Study Drug/Medication (l)(s)	X	X		
Study Drug/Medication Accountability	X	X	X	
Paper Diaries Dispensed (m)	X	X		

Procedure	Open-label Extension(n)(p)			Follow-up Phase(p)(q)
	Day 63 (+/- 2 days)	Day 91 (+/- 2 days)	Day 119 (- 2 / +5 days)/ EOT Visit	2-Week Follow-up (day 133) post last dose (- 2/+7 days)(k)
	Visit 6	Visit 7	Visit 8	
Pain Paper Diary returned/reviewed for completeness	X	X	X	

(l) If subject entering Open-label extension, dispense Open-label study drug/medication at day 35.

(n) While on-study, all visit windows are used for scheduling purposes and all efforts should be made to return subjects to their original visit schedule by calculating the visit window interval from the Baseline/Randomization Visit.

(p) All randomized subjects who discontinue early from the Open-label Extension Phase should complete the EOT Visit and return for the 14-day follow-up safety visit.

(q) For subjects who enter the Open-label Extension Phase, the follow-up visit should be scheduled based on date of their EOT Visit. The visit window for the Follow-up Week 2 Visit is 14 days (- 2/+7 days)

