### **3.5.5     Follow-up Safety Visit (14 days post last dose)**

All randomized subjects should complete the 2 Week Follow-up Safety Visit (regardless of completing the Double-blind Treatment Phase), except those who discontinue early from the Double-blind Treatment Phase due to withdrawal by subject, are lost to follow-up or death. Subjects will return to the study site 14 days after the Day 119 visit/EOT visit or early discontinuation visit (-2/+7 days) to collect laboratory tests, vital signs/physical measurements, physical exam, electrocardiography, assessment of AEs/SAEs, urine pregnancy test, pain rating scales, and Sheehan Suicidality Tracking Scale (S-STS). Subjects will return the concomitant medication paper diary which should be reviewed one final time by study staff. Investigators should assess subjects for AEs consistent with drug dependency or withdrawal effects and report as appropriate.

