Frequency tables of post-DBT pre-OL rimegepant AEs are provided for the interim treated analysis set by SOC and PT for the following endpoints:

- AEs by intensity
- SAEs
- AEs leading to study drug discontinuation.

AEs with a start date after the last dose date/time of DB + 7 and before the OL rimegepant start date is considered to be in the post-DB Pre-OL rimegepant analysis period.

6.4.1.7 *Follow-up AEs*

Frequency tables of follow-up AEs are provided by SOC and PT for the follow-up treated analysis set for the following endpoints:

- AEs by intensity

- SAEs.

For subjects who did not continue into the OL rimegepant period, AEs with a start date after the last dose date/time of DB + 7 is considered to be in the follow-up analysis period. For subjects who continued into the OL rimegepant period, AEs with a start date after the last dose date/time of OL rimegepant + 7 days is considered to be in the follow-up analysis period.

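### Protocol 8.2 ends all-cause SAE collection at End of Treatment, while Table 1 footnote (e) runs it to the 14-day follow-up visit, so SAE counts after End of Treatment could be too low.

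*Protocol*

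**What the plan says.** Two collection rules for SAEs stand in the current protocol.

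- **Protocol 8.2** has all SAEs, related or not, collected from consent and "throughout the course of the study up to and including the End of Treatment Visit". For later events it narrows the request: "The investigator should report any SAE occurring after these time periods that is believed to be related to study drug/medication or protocol-specific procedures".
- **Protocol Table 1, footnote (e)** sets a later end and no causality condition: "SAEs should be reported from signing of consent through the 14 day follow up safety visit". For the milder events the same footnote adds: "Non-serious AEs should be reported from the baseline visit to the safety follow up visit".

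Two other places agree with the footnote. Table 2 marks the row "Serious Adverse Event Assessment" at the 2-week follow-up as well as at Visits 6 to 8. Section 3.5.5 includes in that visit "assessment of AEs/SAEs, urine pregnancy test, pain rating scales". Neither limits the assessment to related events.

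In the SAP, section 6.4.1.7 plans output for the follow-up period: "Frequency tables of follow-up AEs are provided by SOC and PT for the follow-up treated analysis set", with SAEs as one of the two endpoints. Sections 6.4.1.3 and 6.4.1.4 also tabulate SAEs, in on-treatment windows that run past the last dose by about 7 days. None of these sections mentions a causality restriction on the SAEs counted.

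**The concern.** The section whose title covers SAE collection and reporting stops all-cause collection one visit earlier than the schedule of assessments does. No text ranks one above the other, so two sites can both comply with the protocol and collect different data after End of Treatment.

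A site working from 8.2 would apply the investigator's causality judgement before an SAE is recorded. A site working from the footnote would record the SAE first and attribute it afterwards. The SAP tables would pool the two. The practice at issue is a safety one: the protocol uses no data monitoring committee (section 10.2) and relies on the sites, and section 3.5.5 asks investigators to look for dependency and withdrawal effects at this same visit. At stake is the completeness of SAE counts late in the on-treatment window and in follow-up. The efficacy results are not involved.

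**Working it through.** The plan gives no figure to reproduce. The check sets the collection windows beside the SAP analysis windows and counts days.

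**Inputs**

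- End of all-cause collection under 8.2: End of Treatment visit.
- End under footnote (e): follow-up visit, 14 days after End of Treatment, window -2/+7 days (Table 1 footnote (k), Table 2 footnote (q)).
- End of Treatment: Day 35 for a patient who does not enter the open-label extension (OLE), since section 3.5.3 has the End of Treatment schedule completed then; Day 119 for one who does.
- SAP 6.4.1.3: on-DBT (double-blind treatment) period 2 runs to the earlier of last double-blind dose + 7 days and the day before the first OLE dose.
- SAP 6.4.1.4: the on-OL period runs to before last OLE dose + 7 days.
- SAP 6.4.1.7: follow-up starts after last dose + 7 days.
- Assumption: last dose and End of Treatment fall on the same day.

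**Length of the gap between the two rules**

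Nominal: 14 days. Shortest: 14 - 2 = 12. Longest: 14 + 7 = 21.

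**Where those days fall in the SAP**

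| | No OLE | With OLE |
|---|---|---|
| All-cause collection ends under 8.2 | Day 35 | Day 119 |
| Ends under footnote (e), nominal | 35 + 14 = Day 49 | 119 + 14 = Day 133 |
| With the visit window | Day 47 to 56 | Day 131 to 140 |
| Part in the on-treatment window | Days 36-42 (7 days) | from Day 120, to about Day 126 (7 days) |
| Part in the follow-up period, nominal | Days 43-49 (7 days) | Days 127-133 (7 days) |
| Follow-up part with the visit window | 12 - 7 = 5 to 21 - 7 = 14 days | 5 to 14 days |

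The on-OL window is worded to end before last dose + 7. Read literally it holds Days 120-125 (6 days), and Day 126 belongs to neither period. This does not change the conclusion.

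**What 8.2 alone would leave in the tables**

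The whole SAP follow-up period lies after all-cause collection has stopped. Its SAE table could then hold only events that investigators attributed to treatment or to a study procedure. The last 7 days or so of the on-treatment window are affected in the same way. In the double-blind phase only the tail of period 2 is exposed, because the washout after period 1 lies before End of Treatment.

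**The case against.** The strongest reply is that the schedule already settles practice. Footnote (e), Table 2 and section 3.5.5 all put SAE assessment at the follow-up visit, and 8.2 itself requires SAEs, related or not, to be reported within 24 hours of awareness. Much of this stands: a site that runs the visit as scheduled would probably record the events. The 24-hour sentence does not remove the conflict, however. It governs how fast to report, and the same section gives an explicit end to collection and an explicit causality condition after it.

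The consequence is also limited. Protocol 3.2 confines the secondary safety endpoint to the randomization phase. Deaths are listed for enrolled subjects whatever their onset (Protocol 9.4.6), and the SAP draws them from the study termination form as well as the AE form (6.4.1.1). Related and procedure-related SAEs are still reported after End of Treatment. These points stand and keep the matter modest.

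A reader might infer more than the documents support:

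- **That 8.2 overrides the schedule, so events will be missing.** Nothing gives 8.2 precedence, and how sites behaved cannot be known from these documents.
- **That the protocol collects non-serious AEs for longer than SAEs.** Section 8.2 gives no end for non-serious AEs, nor does 8.3.1 give a cut-off date. The end comes from footnote (e), which carries SAEs just as far. The anomaly arises only if a site takes one rule from each place.
- **That the follow-up table loses 14 days, or 29% and 11% of observation.** About half of the nominal 14 days falls in the on-treatment window. The shares 14/49 = 28.6% and 14/133 = 10.5% leave out the 14 to 30 days of screening, when both rules collect all SAEs. With screening they are 14/63 = 22% to 14/79 = 18%, and 14/147 = 9.5% to 14/163 = 8.6%. Even these describe exposure of unrelated SAEs only.
- **That the SAP asserts complete follow-up data.** It lists tables and makes no statement on completeness.

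**Conclusion.** The inconsistency is real and sits in current text. For a nominal 14 days after End of Treatment (12 to 21 with the visit window), SAEs judged unrelated are required under footnote (e) and not under 8.2. If last dose and End of Treatment coincide, about 7 of those days belong to the SAP on-treatment window (on-DBT period 2 without the OLE, on-OL with it) and about 7 (5 to 14) to the follow-up period. SAE counts in both could be too low.

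The split rests on that same-day assumption: if dosing stopped before the End of Treatment visit, more of the gap moves into follow-up. The number of events at risk cannot be estimated, because the documents give no SAE rate and do not show which rule sites used.

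This is a risk of undercounting. It is not evidence of clear bias between treatments: each treatment occupies period 2 in one of two sequences randomized 1:1, and the OLE has a single treatment. The point deserves correction because it affects the completeness of safety tables; it does not touch the primary result.

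**What to change.** Reconcile 8.2 with footnote (e), Table 2 and section 3.5.5. Change the end point of all-cause SAE collection in 8.2 to include the 14-day Follow-up Safety Visit, and keep the related-only request for events after that visit. This is one sentence and adds no visit or assessment.

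A protocol change alone cannot alter what has been recorded, since SAP section 1 says the study was terminated early in 1Q2023. The SAP or study report should therefore also:

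- state which collection rule sites applied after End of Treatment, and whether it varied by site;
- footnote the follow-up SAE table, and the on-treatment SAE tables for the days after the last dose, to say whether SAEs judged unrelated were collected throughout.

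The cost is a query to the sites or monitors and a few lines of text. No analysis needs to be redesigned.
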